
Thus, the debate continues regarding the role of fibrinolytics in the management of pleural collections. Most intensivists have observed effective eradication of early empyema in some patients but agree that the appropriate population remains

ill defined. On the basis of the pathophysiology of empyema and the morbidity of thoracotomy for delayed intervention, most think that fibrinolytic treatment should be attempted for early empyema with simple collections separated by thin septa documented by CT scan if tube thoracotomy drainage fails. Image-guided direct infusion of fibrinolytics into the collection is superior to delivery via the failed chest tube. The precise agent, dosage, and timing of infusion remain to be analyzed; the combination of tPA and DNase seems to be the most effective regimen at this time.(52) Large case series have emerged since the publication of MIST II. Piccolo et al(53) reported a three-year experience using the MIST II protocol (5mg DNase and 10mg tPA BID for up to six doses) in 10 different centers. Inclusion criteria were patients with a pleural PH < 7.2 and clinical evidence of infection. The majority of these patients were male (69%) had CAP (97%), middle aged (median 56 yrs.), and received 2 days of therapy. Of the 107 patients included in the analysis 93% had successful fibrinolytic/DNase to avoid surgery. Of note 23% of patients had increased pain associated with infusion and required additional analgesic medication, which should be taken into consideration when starting therapy. A smaller case series from Mehta et al.(54) evaluating 55 patients using once a day therapy for 3 days had similarly positive results with 93% of patients not requiring surgical intervention. They also appreciated that 15% of patients required additional analgesics during treatments.

Surgical Decortication

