Covariates: Age, BMI, Diabetes, Duration of symptoms, Steroid use
Adverse events: Air leak, bleeding requiring transfusion, need for additional chest tube, and need for secondary operation/intervention, mortality

B. Description of Population to be Enrolled:

Adults ≥ 18 admitted with pleural effusion diagnosed by chest x-ray or computed tomography, that undergo thoracentesis or chest tube drainage by any service.

If the patient has a pleural fluid PH < 7.3 , the patient will be screened for potential study enrollment. If the patient does not have any exclusion criteria (listed below) the patient will be followed for study enrollment. If there is a persistent effusion 24 hours after chest tube insertion, diagnosed by morning chest X ray, and no exclusion criteria identified, the patient may then undergo CT scan to characterize the effusion. If CT scan is done and confirms a loculated fluid collection or if an additional CXR is grossly abnormal, despite chest tube drainage, these patients will then be approached for consent and randomized to either bedside fibrinolytic therapy through their chest tube versus operative VATS decortication. The patients that undergo VATS decortication, will subsequently be transferred to the surgery service for the remainder of their hospital stay.

Exclusion:

- Intrathoracic malignancy
- Any existing malignancy causing malignant effusion
- Prehospital pulmonary symptoms over 14 days prior to admission
- Prior instrumentation of the chest during same admission
- Malignant cells from initial pleural fluid sample
- End stage liver disease (Child's B or greater)
- Coagulopathy
- Unable to tolerate surgical procedure
- Frank purulent drainage (needs OR regardless)
- Recent surgery of abdomen or thorax precluding the use of tPA
- Pre-existing and permanent neurologic impairment

C. Study Design and Research Methods

This study is a proposed pragmatic prospective randomized open label clinical trial to treat patients with complicated parapneumonic effusion. Complicated parapneumonic effusion is defined as fluid collection in the pleural space with a fluid pH < 7.3 .

Standard of Care Procedure prior to study eligibility:

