Eligible patients will be screened for study participation and after consenting will be randomized to early surgical decortication via VATs versus fibrinolytic therapy (FT) based off of the current MIST II protocol, currently utilized at Denver Health. Should the patient be randomized into the FT group, initiation of fibrinolytic therapy will start within 24 hours of CT scan. Conversely, if the patient is randomized into the surgery group, VATS decortication will occur as soon as the operating room is available. The fibrinolytic therapy will be delivered by a member of the treatment team per current standard of care for 3 days. Removal of chest tubes is dependent on the mutual agreement of both the surgical and pulmonary attending involved with the patients care. Per standard clinical care, labs will be collected daily (determined by the medical team, but usually include complete blood count and basic metabolic panel). In addition to the standard of care labs, pleural fluid will be collected for study purposes and extra blood samples will be collected for thrombelastography (TEG) analysis. TEG assesses changes in clot strength in both plasma and pleural samples by measuring proteins related to coagulation with proteomic analysis. Thrombo Therapeutics, Inc. is not involved in this study. tPA-challenged TEG assay is used for research purposes only. The data from this test is not accessible for the clinical care providers and does not affect the patient care. We are using this assay to study the clot sensitivity and as a marker for massive blood transfusion. The results of tPA-challenged TEG assay will not be used for any clinical decision or research subject assignment. At the moment there is no plan to submit tPA-challenged TEG data to the FDA. This study blood and pleural fluid will be drawn by the phlebotomy service or medical team member (nurse or physician to draw pleural fluid) and will be collected by a professional research assistant (PRA) trained in both running the TEG assay and in processing of blood for plasma analysis. Blood and pleural fluid samples will be 3.5ml each.

Study blood will be drawn prior the intervention and then for 3 sequential days after (for a total of 4 draws). This blood will be assayed by TEG with and without the t-PA challenge. This modified TEG assay (t-PA challenge) is completed by taking 500 microliters of patient blood out of the citrated tube and adding it to a pre made

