glass container with lyophilized t-PA. This blood is mixed with a defined concentration of t-PA is then added to a TEG cup for analysis. This will quantify the patient's systemic blood to fibrinolysis resistance. In addition to the blood draws, pleural fluid will be drawn from the patient's chest tube in the morning prior to the intervention, and then after the intervention for 3 days (same days that blood samples are obtained, for a total of 4 pleural fluid samples). Pleural fluid samples will only be drawn from chest tubes already in place. In the event the chest tube is removed prior to 3 days post-intervention pleural fluid samples will be unattainable. The pleural fluid would otherwise be discarded as human waste. We will also conduct a novel assay to determine if the pleural space content is fibrinolytic resistant. This will be accomplished by an ex vivo diluting of the patient's blood (from the collected citrated tube) by 25% with normal saline and conducting a t-PA challenge versus a 25% dilution of the patient's blood (from the collected citrated tube) with their pleural fluid. The relative differences in the lysis at 30 minutes between these two assays will give a crude estimate of fibrinolytic inhibition. Remaining blood after TEG analysis will be spun down to plasma and flash frozen for future measurements, such as elastase activity and a targeted cohort for proteins related to coagulation with proteomic analysis. These results paired with proteomic analysis will enable correlations between fibrinolysis resistance and relative protein concentrations to identify potential mechanistic culprits driving fibrinolysis resistance. This study blood will be collected by PRA (drawn by the nurse and handed off to the PRA) trained in both running the TEG assay and in processing blood for plasma analysis.

Data collection will be done prospectively by a member of the research team. Data

will be stored in a secure excel sheet accessible only to the study team members.
Randomization

Intervention

VATS decortication
Vs.
tPA and DNASE per MISTII protocol

D. Description, Risks and Justification of Procedures and Data Collection Tools:

The adverse events of the standard of care fibrinolytic therapy include pain, fever, bleeding, and failure to effectively clear infection from the pleural space requiring

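### In patients given intrapleural tPA, pleural-fluid lysis measured after treatment starts is confounded by residual drug and biased toward less fibrinolytic inhibition

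*Combined protocol and SAP*

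**What the plan says.** **Treatment.** Under Section IV.B, eligible patients are "randomized to either bedside fibrinolytic therapy through their chest tube versus operative VATS decortication". The intervention list in IV.C gives the drug as "tPA and DNASE per MISTII protocol", and the same section adds: "The fibrinolytic therapy will be delivered by a member of the treatment team per current standard of care for 3 days". The background (Section II), describing a case series that used the MIST II regimen, gives it as "5mg DNase and 10mg tPA BID for up to six doses".

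**Sampling.** IV.C has pleural fluid drawn from the chest tube "in the morning prior to the intervention, and then after the intervention for 3 days", on the same days as the study blood. That makes four pleural samples, taken only from tubes already in place, and none once the tube is out.

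**Assay.** Blood diluted by 25% with saline and challenged with t-PA is compared with blood diluted by 25% with the patient's pleural fluid. IV.C then states: "The relative differences in the lysis at 30 minutes between these two assays will give a crude estimate of fibrinolytic inhibition". It adds that these results, paired with proteomics, "will enable correlations between fibrinolysis resistance and relative protein concentrations".

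**Analysis.** IV.C names neither the time points at which this assay is run nor a between-arm test for it. Aim 5 (Section I) covers coagulation status during each intervention. IV.A lists change in TEG variables once the intervention has begun as a secondary outcome. IV.F describes t, Mann-Whitney and chi-square tests between arms for outcomes in general. IV.F also expects that up to 30% may decline surgery, and plans analyses both by intention to treat and by treatment received.

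**The concern.** The therapeutic agent in one arm is also the reagent of the assay. It is put into the space that supplies the test fluid, on days that overlap with sampling. The assay is meant to show how strongly the pleural contents resist fibrinolysis. If the fluid still carries active drug, the reading is resistance net of that drug.

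The plan contains no safeguard: no sampling time relative to a dose, no washout, no measurement or neutralisation of residual tPA, and no restriction of the assay to the pre-intervention sample.

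At stake is the mechanistic result. A fall in apparent inhibition after fibrinolytic but not after VATS could be reported as a biological effect of treatment when it is partly, or wholly, carry-over. A protein correlation that included such values would mix drug exposure with endogenous resistance. The bias follows treatment, so more samples would not average it out.

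**Working it through.** The plan states no figure for this point, so there is none to reproduce. The check has four steps.

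**1. Schedules side by side**

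| Pleural sample | Patient given fibrinolytic | Patient given VATS and no fibrinolytic |
|---|---|---|
| Before intervention | no instilled tPA | no instilled tPA |
| Three days after (if tube still in) | within or at the end of the 3-day course | no instilled tPA |

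This takes the post-intervention days to run from the start of treatment, as the TEG outcome in IV.A indicates. At most 3 of 4 samples are exposed, fewer if the tube comes out early.

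**2. Direction**

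Let S be lysis in the saline mix and P the lysis the pleural mix would show without drug. The relative difference is I = (S − P)/S. Residual active tPA changes P to P + d, with d ≥ 0. Both mixes use the same citrated blood, so anything circulating is common to both; only the diluent differs. The observed value is

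I* = (S − P − d)/S = I − d/S.

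So I* ≤ I: inhibition is understated, and I* is negative if d exceeds S − P. The text does not make clear whether the pleural mix also receives the t-PA challenge. The sign of the bias is the same either way.

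**3. Possible size**

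tPA in the mix after one dose = 10,000,000 ng ÷ V × f × 0.25, where

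- 10 mg is the dose in the Section II background;
- 0.25 is the pleural share of the mix, reading 25% as a share of the final volume;
- V (pleural volume) and f (fraction still active) are assumptions, as the documents give neither. The values 395 and 850 are rounded from the streptokinase column of the paediatric table in IV.F (drainage 394.93 and 850.59, taken as mL).

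| V (mL) | f = 100% | f = 10% | f = 1% | f = 0.1% |
|---|---|---|---|---|
| 100 | 25,000 | 2,500 | 250 | 25 |
| 395 | 6,329 | 633 | 63 | 6.3 |
| 850 | 2,941 | 294 | 29 | 2.9 |
| 2,000 | 1,250 | 125 | 12.5 | 1.25 |

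(ng/mL in the mix.) The range is 1.25 to 25,000 ng/mL. IV.C calls the challenge concentration defined but does not state it, so these figures cannot be turned into a bias in lysis.

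**4. Effect of patients who decline surgery**

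Let b be the average of d/S in exposed samples. Suppose 30% of those assigned to VATS decline, all of them receive fibrinolytic, and b is the same for them. The intention-to-treat contrast is then biased by b × (1 − 0.30) = 0.70b, and a contrast by treatment received by the full b. Neither analysis removes the bias.

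**The case against.** The strongest case against is that much of the problem has to be inferred. IV.C schedules four pleural draws but does not say that the assay is run on all of them, and it specifies no between-arm test. Aims 2 to 4 are worded as contrasts and Aim 5 is not. The protocol itself calls the assay novel and its estimate crude. The protein correlation may use the systemic blood result rather than the pleural one. The days after the intervention could mean days after the full course, which would reduce the overlap. TEG results do not guide care, and the primary outcome is length of stay.

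Most of this stands as a limit on the claim. It does not remove it. Nothing restricts the assay to baseline, and Aim 5, the IV.A outcome and the general tests in IV.F leave a post-treatment between-arm comparison open. Crude suggests imprecision, whereas this is a one-sided bias tied to treatment.

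Three stronger readings are tempting and are not supported:

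- **That the assay simply measures the drug after treatment.** This needs residual tPA to dominate, and the range in the working is too wide to show that.
- **That three samples are always affected.** Three is a maximum, because sampling ends when the tube is removed.
- **That the VATS arm is free of the problem.** This holds by treatment received, not by assignment: patients who decline surgery and receive fibrinolytic carry it too. Nor is post-VATS drainage a clean reference, since Section II says the tubes clear debris and blood from the procedure.

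**Conclusion.** The point holds as a confounding problem of known direction and unknown size. In patients who receive intrapleural tPA, up to three of four pleural samples may contain active drug, and the inhibition estimate is then biased toward less inhibition. The conclusion assumes that post-intervention sampling overlaps or closely follows dosing, that some tPA is still active when fluid is drawn, and that the assay is run on those samples. The documents support the first and leave the other two open.

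The pre-intervention sample is unaffected in both arms, so the assay can still describe baseline pleural resistance. This is a minor improvement to a mechanistic result and has no bearing on the primary outcome.

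**What to change.** Add to Section IV.F:

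- The pleural inhibition estimate, and any protein correlation that uses it, is based on the pre-intervention sample, pooled over arms.
- Post-intervention pleural lysis is reported descriptively only, grouped by treatment actually received (any fibrinolytic versus VATS without fibrinolytic), with time since last dose where recorded.
- A between-arm difference in post-intervention pleural lysis is not interpreted as a difference in endogenous fibrinolysis resistance.

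IV.C should also say at which time points the assay is run, whether the pleural mix is challenged, and whether the three days count from the start or the end of the intervention.

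The cost is wording. The longitudinal between-arm pleural comparison is given up as an inferential result, but it could not have been read as endogenous resistance. Samples and treatment do not change.

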This study is established as a pragmatic study as it is anticipated that some patients would prefer conservative fibrinolytic therapy to surgery. We have adjusted for this in our power calculation (see below). In addition the timing of availability of the operating room staff is not predictable. There may be a delay in taking the patient to the operating room. The importance of performing this study is that it is perceived that fibrinolytic therapy should be the standard of care for treating these patients. However, pediatric literature supports that optimal care of these patients may be an early surgical intervention. This is similar to an operative intervention for appendicitis. While it is possible to treat patients with appendicitis with antibiotics and avoid surgery, it results in longer hospitalizations, in addition if medical treatment fails the appendical perforation can result in life threatening sepsis and require surgery or additional procedures. This parallels complicated parapneumonic infections, in which surgery can be avoided, but result in prolonged hospitalization and if fibrinolytic therapy fails, surgery becomes a riskier endeavor.

F. Data Analysis Plan:

Power analysis

Using the pediatric literature assume effect size of reduction in 3 days of hospitalization requirement with variability of 2.3 days with alpha of 0.05 and 1:1 group allocation would require 12 patients per arm (24 total) to power the study to 80%. Anticipating up to 30% of patients may decline surgery we would seek to enroll 17 patients per arm. Will conduct an analysis based on intention to treat (included patients who declined surgery) in addition the treatment the patients received.

	STK	VATS	P
Post-therapy days of O ² support	2.3±1.4	2.1±2.0	0.911
Afebrile days after intervention	3.9±2.1	3.4±2.4	0.782
Analgesia doses	22.1±18.9	25.4±13.1	0.561
Chest tube removal time	9.48±2.50	6.56±1.55	0.0001
Duration of hospital stay	10.37± 2.29	7.41±1.45	0.0001
Duration of symptoms after intervention	6.78±1.69	3.78±1.25	0.0001
Fluid drainage			
Initial drainage amount	394.93±220.65	379.19±230.14	0.786
Postoperative drainage amount	850.59±301.91	865.78±444.41	0.884

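### Raising 12 to 17 per arm does not offset up to 30% of patients declining surgery: if decliners receive fibrinolysis, intention-to-treat power falls below 80% near that bound, and willingness to accept either arm is not asked before randomisation

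*Combined protocol and SAP*

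**What the plan says.** Section IV.E (Potential Scientific Problems) calls the trial pragmatic because "it is anticipated that some patients would prefer conservative fibrinolytic therapy to surgery", and says that the power calculation takes this into account. Section IV.F (Power analysis) derives 12 per arm for 80% power and continues: "Anticipating up to 30% of patients may decline surgery we would seek to enroll 17 patients per arm". The same paragraph plans two analyses. One is by intention to treat (ITT) and keeps patients who declined surgery; the other is by treatment received. Neither is named as primary.

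On the order of events, IV.C (Study Procedures) states: "Eligible patients will be screened for study participation and after consenting will be randomized to early surgical decortication via VATs versus fibrinolytic therapy". Consent therefore comes before allocation. The nearest eligibility criterion in IV.B is the exclusion "Unable to tolerate surgical procedure", which concerns fitness. No criterion concerns willingness. The protocol does not say what treatment a patient who declines surgery receives.

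**The concern.** Because ITT is defined to include patients who declined surgery, decliners are randomised patients who stay in the analysis. They are not people who refused consent. Dividing by one minus the refusal rate replaces patients whose data are lost. It does not restore a treatment difference that shrinks because part of the VATS arm did not have VATS.

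At stake is the primary comparison of length of stay. With substantial refusal, ITT may lack the stated power. The treatment-received analysis would compare groups formed partly by patient preference, so it could not stand in as the randomised answer. Part of the refusal may also be avoidable, since preference can be asked at consent, before allocation.

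**Working it through.** **Inputs (IV.F).** The plan says "assume effect size of reduction in 3 days of hospitalization requirement" "with variability of 2.3 days", "with alpha of 0.05 and 1:1 group allocation", with a power target of 80%. I read the variability as a common SD. Sidedness is not stated; I take two-sided.

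**The plan's own figures.** For 80% power with a 3-day difference and SD 2.3, the normal approximation gives 10 per arm and the t test 10.3, so 11. Dividing 10.28 by 0.864, the worst-case efficiency of the Mann–Whitney test, gives 11.9, so 12. The stated 12 is sound and slightly conservative: the t test at 12 per arm has 86% power. The inflation is 12/0.7 = 17.1, reported as 17.

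**ITT power with refusal.** Let c be the share of the VATS arm that declines. Assume decliners receive fibrinolysis and have that arm's outcome.

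- Expected ITT difference: 3 × (1 − c). At c = 0.30 this is 2.1 days.
- VATS-arm variance as a mixture: 2.3² + 3² × c(1 − c). At c = 0.30 this is 5.29 + 1.89 = 7.18, an SD of 2.68.
- Standard error at 17 per arm, c = 0.30: 2.3 × √(2/17) = 0.79 with a common SD, or √((5.29 + 7.18)/17) = 0.86 with the mixture.

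Power of a two-sided t test at 17 per arm:

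| Refusal in VATS arm | ITT difference (days) | Common SD | Mixture variance |
|---|---|---|---|
| 0% | 3.0 | 96% | 96% |
| 10% | 2.7 | 91% | 89% |
| 20% | 2.4 | 84% | 79% |
| 30% | 2.1 | 73% | 66% |

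Simulation with 200,000 replicates also gives 66% for the last cell. Restoring 80% at 30% refusal by numbers alone needs 20 per arm (common SD) to 24 per arm (mixture).

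**Treatment-received analysis.** With 30% of 17 declining, about 5 patients move, giving roughly 12 against 22. Those who move have chosen to do so.

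**Effect of asking about willingness first.** Take 34 patients approached, of whom 30% (34 × 0.3 = 10.2) would refuse surgery. If a fraction f of these is identified and not randomised, 34 − 10.2f remain, and the refusal share among them is 10.2(1 − f)/(34 − 10.2f). Group sizes are rounded to the nearest whole number; power is by simulation.

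| Refusers identified | Per arm | Residual refusal | Power |
|---|---|---|---|
| None (as written) | 17 | 30% | 66% |
| A quarter | 16 | 24% | 71% |
| Half | 14 | 18% | 73% |
| Three quarters | 13 | 10% | 79% |
| All | 12 | 0% | 86% |

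**Accrual.** IV.D expects 2 eligible patients per month and completion within 18 months. If those 2 include refusers and all refusers are screened out, 1.4 per month are randomised: 24/1.4 = 17 months for 12 per arm, or 34/1.4 = 24 months for 17 per arm.

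**The case against.** The strongest reply is that the protocol discloses the problem, calls the design pragmatic because of it, adds patients and plans ITT. The effect of a policy of offering surgery is a legitimate target, and the Background frames the question around fitness for surgery. That stands as a defence of the design. It does not rescue the sample size, because a policy-of-offer effect at 30% refusal would be about 2.1 days and the calculation uses 3.

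Second, 30% is an upper bound. At 20% refusal the plan is about on target and at 10% it exceeds it. With the paediatric table's own figures (difference 2.96 days, SDs 2.29 and 1.45, decliners given the fibrinolytic-arm SD), simulated power is 86% at 20% and 73% at 30%. This stands: the shortfall is confined to the upper part of the range.

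Third, agreeing to be randomised ordinarily implies accepting either arm, and some refusals will be changes of mind after allocation. Consent pages are not in the supplied text, so their wording cannot be checked. A reader might infer that the trial knowingly randomises patients already set on refusing, and that one eligibility line would remove crossover at source. The documents support neither inference: they say only that patients may decline, not when the preference forms. Even at 12 per arm after screening, residual refusal of 5%, 10% or 15% gives 81%, 75% or 69% power. The gain shrinks but does not vanish.

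Finally, randomising fewer patients leaves less information for the complication, cost and coagulation aims. That is a real cost.

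**Conclusion.** The point holds as an under-corrected allowance for refusal combined with a missed opportunity to reduce it. The claim that the power calculation adjusts for refusal is not correct for the ITT analysis. Power at 17 per arm is about 89–91%, 79–84% and 66–73% at 10%, 20% and 30% refusal, so the 80% target fails near the plan's stated upper bound.

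It would go too far to say that the trial is underpowered whatever the refusal rate, or that the issue was overlooked. The lower part of the range is adequately powered, and the protocol names the issue itself.

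The figures rest on four assumptions: a two-sided test, a common SD of 2.3 for each treatment, refusal confined to the VATS arm, and decliners receiving fibrinolysis with that arm's outcome. The protocol states none of the last three outright.

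**What to change.** 1. In IV.E and IV.F, replace the statement that refusal has been adjusted for. Name ITT as the primary analysis, present the treatment-received analysis as supportive, and report ITT power over 0–30% refusal.
2. In IV.B, add a criterion along these lines: *after discussion of both treatments and before randomisation, the patient states willingness to undergo whichever is assigned.* Record those not willing, with the reason, in a screening log and do not randomise them.
3. Keep ITT for anyone who still changes their mind. State the number to be randomised with an explicit allowance for residual refusal; removing the present inflation without this would leave no allowance at all.

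The text changes are small: one criterion, one log field and a revised power paragraph. The real cost is that fewer approached patients are randomised, about 24 of 34 if every refuser is identified at 30%. Keeping 17 per arm would instead take about 24 months against the planned 18, if the expected 2 per month includes refusers. Results would apply to patients willing to have either treatment, and the log would show how many were not.

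### The increase from 12 to 17 per arm replaces lost patients, but patients who decline surgery stay in the intention-to-treat analysis; at 30% refusal its power is about 66–76%, not 80%

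*Combined protocol and SAP*

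**What the plan says.** Section IV.F (Data Analysis Plan, Power analysis) takes its assumptions from a paediatric trial: "assume effect size of reduction in 3 days of hospitalization requirement", "with variability of 2.3 days", "with alpha of 0.05 and 1:1 group allocation". It arrives at 12 per arm for 80% power. It then adds: "Anticipating up to 30% of patients may decline surgery we would seek to enroll 17 patients per arm".

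The next sentence fixes who is analysed: "Will conduct an analysis based on intention to treat (included patients who declined surgery) in addition the treatment the patients received". Neither of these two analyses is called primary, there or in the statistical methods paragraph that follows.

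Section IV.E (Potential Scientific Problems) gives the reason for the allowance, namely that "it is anticipated that some patients would prefer conservative fibrinolytic therapy to surgery", and tells the reader that "We have adjusted for this in our power calculation (see below".

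**The concern.** Dividing a sample size by one minus a rate compensates for patients whose data are lost. Here the data are not lost. A patient randomised to VATS who declines it is still counted in the VATS arm under ITT, and IV.E implies that this patient receives fibrinolysis. The ITT sample therefore stays at 17 against 17 while the difference between the arms shrinks. The sample size makes no allowance for that shrinkage: the 3-day effect is carried through unchanged. The assurance in IV.E is therefore not correct for ITT at the refusal rate the plan chose.

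ITT is the comparison that randomisation protects. In an open-label trial whose primary outcome is the treating team's judgement of fitness for discharge, leaving open which of two analyses leads is a real weakness, because the two can disagree in exactly the situation the plan anticipates.

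**Working it through.** **Inputs.** From IV.F: difference 3 days, SD 2.3, alpha 0.05, 1:1 allocation, 80% power, 12 per arm raised to 17, refusal up to 30%, t test or Mann-Whitney. From the table in IV.F, hospital stay was 10.37 ± 2.29 days (fibrinolysis) and 7.41 ± 1.45 (VATS), a difference of 2.96. Assumed: a two-sided test (sidedness is not stated), the 30% applies to the VATS arm, every decliner receives fibrinolysis, decliners have the fibrinolysis-arm mean stay, and nobody crosses over the other way.

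**1. The plan's own figures.** Normal approximation: n = 2 × (1.96 + 0.84)² × 2.3² / 3² = 9.2, so 10 per arm. The t test needs 11 (power 83%). At 12 per arm t-test power is 86%, so 12 is slightly generous. The inflation is 12 / (1 − 0.30) = 17.1, taken as 17. With no refusal, 17 per arm gives 96%.

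**2. Dilution.** Expected ITT difference = 0.7 × 3 + 0.3 × 0 = 2.1 days.

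**3. Spread in the VATS arm.** The arm becomes a mixture of two groups with different means, which adds variance.
- (a) SD 2.3 under both treatments: √(2.3² + 0.3 × 0.7 × 3²) = 2.68.
- (b) SD simply held at 2.3, ignoring the mixture.
- (c) Table SDs: √(0.7 × 1.45² + 0.3 × 2.29² + 0.21 × 2.96²) = 2.21.
- (d) As (b), by normal approximation: Φ(2.1/2.3 × √8.5 − 1.96) = 76%.

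**4. ITT power at 17 per arm.** Cases (a) and (c) are simulated t tests; (b) is the noncentral t.

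| Case | 10% decline | 20% decline | 30% decline | Refusal at which power is 80% | Treated effect with 80% power at 30% refusal | n per arm for 80% at 30% refusal |
|---|---|---|---|---|---|---|
| (a) | 89% | 79% | 66% | 19% | 3.7 days | 24 |
| (b) | 91% | 84% | 73% | 24% | 3.3 days | 20 |
| (c) | 95% | 86% | 73–74% | 25% | 3.3 days | 20 |
| (d) | 93% | 86% | 76% | 26% | 3.2 days | 19 |

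The Mann-Whitney test, which the plan allows, gives about 64–65% under (a) and 75% under (c) at 30% refusal.

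**5. Chance variation in the number of decliners.** With exactly 5 of 17 declining (29%), power is 68% under (a) and 76% under (c), so this variation does not explain the shortfall.

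**6. Disagreement between the two analyses at 30% refusal.** ITT is non-significant while treatment-received is significant in 28% of simulated trials under (a) and 25–26% under (c). Both are significant in about 65% and 73–74%. These figures assume that those who decline do not differ in prognosis from those who accept.

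**The case against.** **The plan attaches 80% to 12 per arm, and never says in terms that ITT has 80% power at 17 with 30% declining.** That is so. For the treatment-received analysis the inflation does its job: 17 × 0.7 = 11.9, so about 12 patients have VATS, and nominal power is about 94% or more. But IV.E says the refusal problem has been adjusted for without limiting that to one analysis, and the comparison it does serve is not randomised, because patients choose whether to have surgery.

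**Thirty percent is a ceiling.** With exactly 3 decliners power is about 83–90%, and with 4 about 76–84%, so the shortfall turns on one or two patients. This limits the size of the problem. It does not remove it, because the sample size was set to that ceiling.

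**The 66% end is conservative.** It applies the larger of the two table SDs to both treatments before adding mixture variance. The table's own SDs give 73–74%, which is still below 80%. Power exceeds 80% only with the pooled table SD of 1.92 and no mixture variance (86–88%). That is not the plan's SD, and it ignores the spread that decliners add.

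**All these figures depend on a paediatric SD.** This stands. The adult series in section III (operative mean 24 days, 95% CI 17 to 31, 26 patients) implies an SD near 7/2.06 × √26 = 17 days. That cohort and its measure of stay differ from this trial's, so 17 need not apply. But an assumed SD of 4 would give about 56% with no refusal and 32% for a 2.1-day difference. The restated power must therefore be labelled as conditional on the SD.

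**Refusal might happen before randomisation.** Such patients would have no assigned arm and could not be in an ITT set, where the plan expressly puts decliners.

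**Conclusion.** The concern holds. The step from 12 to 17 per arm allows for lost patients, not for the dilution that decliners cause when they are kept in the ITT analysis. At the plan's own 30% allowance, ITT power for a 3-day effect among treated patients is about 66–76%, and marginally lower (64–65%) by Mann-Whitney in the least favourable case. Power of 80% is kept up to about 19–26% refusal. At 10% refusal it is comfortably above 80%.

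The result rests on a two-sided test, on decliners receiving fibrinolysis (implied by IV.E), on their having that arm's mean stay (not stated in the documents), and on the paediatric SDs. The shortfall is moderate and arises near the ceiling. The statement that refusal has been adjusted for is nevertheless wrong for ITT, and the lack of a named primary analysis should be settled before results are seen.

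**What to change.** Keep 17 per arm and change the wording of IV.E and IV.F:

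- Replace the claim that refusal is adjusted for with a statement of this kind: *If 30% of the VATS arm decline surgery and receive fibrinolysis, the ITT analysis at 17 per arm has about 66–76% power (two-sided 0.05) for a 3-day effect among treated patients, depending on the SD and method, and 80% power for an effect of about 3.2 to 3.7 days. Power is at least 80% if no more than about 19% decline. These figures assume an SD close to the paediatric value of 2.3 days and that decliners have the fibrinolysis-arm mean stay.*
- Name ITT as the primary analysis.
- Label the treatment-received analysis as supportive and non-randomised. A complier-average estimate may be added as a further supportive analysis.

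The cost is protocol wording and a less favourable stated power. Design and sample size do not change, so no power is recovered. For information, restoring 80% at 30% refusal would take about 19 to 24 per arm on the same assumptions.
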